#### 9.5.2.3 Overall Survival

OS is defined as the time from first dose of study medication to death due to any cause. For subjects not known to have died at the end of the study, OS will be censored at the time the subject was last known to be alive (including follow-up data).

### 9.5.3 Other Efficacy Endpoints

#### 9.5.3.1 Quality of Life

The QLQ-C30 is composed of both multi-item scales and single-item measures. These include five functional scales (Physical functioning, Role functioning, Emotional functioning, Cognitive functioning, Social functioning), three symptom scales (Fatigue, Nausea and vomiting, Pain), a global health status / QoL scale, and six single items (Dyspnoea, Insomnia, Appetite loss, Constipation, Diarrhoea, Financial difficulties). Each of the multi-item scales includes a different set of items – no item occurs in more than one scale.

The QLQ-C30 is collected at Cycle 1, Day 1 pretreatment. This will be the baseline measure. The questionnaire is collected on Day 1 of even-numbered cycles thereafter.

All of the scales and single-item measures range in score from 0 to 100. A high scale score represents a higher response level.

Thus a high score for a functional scale represents a high / healthy level of functioning, a high score for the global health status / QoL represents a high QoL, but a high score for a symptom scale / item represents a high level of symptomatology / problems.

The principle for scoring these scales is the same in all cases:

1. Estimate the average of the items that contribute to the scale; this is the raw score.
2. Use a linear transformation to standardize the raw score, so that scores range from 0 to 100; a higher score represents a higher (“better”) level of functioning, or a higher (“worse”) level of symptoms.

SAS coding of the scoring procedure is presented in the scoring manual page 54 of the manual.

Data from the QLQ-C30 will be scored as recommended by the European Organization for Research and Treatment of Cancer and summarized descriptively for the functional scales, symptom scales, individual items, and the global health status. Normalized scores and their changes from baseline will be summarized for functional scales, symptom scales, individual items, and the global health status.

#### 9.5.3.2 Pharmacokinetics and Immunogenicity

Blood samples for PK and ATA assessments will be collected at the time points outlined in Table 4 and 5 in the protocol. Sensitive, qualified assays will be used to measure concentrations of antibody-drug conjugate (ADC) (vadastuximab talirine) and SGD-1882 in plasma and ATA in serum. Remaining PK samples will be archived for possible analysis of SGN-CD33-related species. The assays will include enzyme-linked immunosorbent assays (ELISA) and liquid chromatography/tandem mass spectrometry assays, as well as other assays if further characterization is required. A qualified electrochemiluminescence assay will be used to assess ATA.

Estimates of selected PK parameters (vadastuximab talirine ADC and SGD-1882) and incidence of ATA to vadastuximab talirin will be summarized by phase and treatment arm or dose level.

### 9.5.3.3 Biomarkers

Biomarker assessments may include CD33 expression level, abundance of myeloid-derived suppressor cells (MDSC), characterization of leukocyte subpopulations in peripheral blood mononuclear cells (PBMC), variation in sequence of CD33 and genes commonly mutated in MDS and hematologic malignancies, soluble CD33, abundance of a variety of cytokines, and testing for paroxysmal nocturnal hemoglobinuria (PNH) and HLA-DR15 at protocol-specified time points. Methods of analysis may include flow cytometry, ELISA, deoxyribonucleic acid (DNA), and ribonucleic acid (RNA) sequencing. Biomarker results may be defined and presented in a separate report.

### 9.5.4 Methods for Handling Dropouts and Missing Data

With the exception of time-related endpoints, missing observations will generally be treated as missing at random and will not be imputed, unless otherwise noted.

For time-related endpoints, DOR and PFS will follow [Table 2](#) below:

**Table 2: Kaplan-Meier Analysis Rules**

Situation	Date of Progression or Censoring	Outcome
No baseline and/or post-baseline disease assessment	Date of first dose	Censored
No documented progression	Date of last adequate response assessment (or Study Day 1 in the absence of a post-baseline response assessment)	Censored
PD documented during or between scheduled visits	Date of response assessment demonstrating PD	Event
New subsequent cancer therapy initiated prior to documented progression	Start date of new subsequent cancer therapy	Censored
Death before first PD assessment	Date of death	Event
Death between response assessment visits	Date of death	Event

For concomitant medication dates, see [Section 5](#) for imputation rules. For missing or partial start and stop adverse event dates, see [Appendix 4](#) for imputation rules.

Note that the actual value for date (not imputed) will be presented in all data listings and imputed dates will be used for derivations only.

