18.6 Appendix 6: Response Assessment – International Working Group Response Criteria

Category	Response criteria (responses must last at least 4 weeks)
Complete remission Bone marrow:	≤5% myeloblasts with normal maturation of all cell lines*
	Persistent dysplasia will be noted*†
	Peripheral blood‡
	Hgb ≥11 g/dL
	Platelets ≥100 x10 ⁹ /L
	Neutrophils ≥1.0 x10 ⁹ /L†
	Blasts 0%
Partial remission	All CR criteria if abnormal before treatment except: Bone marrow blasts decreased by ≥50% over pretreatment but still >5% Cellularity and morphology not relevant
Marrow CR†	Bone marrow: ≤5% myeloblasts and decrease by ≥ 50% over pretreatment† Peripheral blood: if HI responses, they will be noted in addition to Marrow CR†
Stable disease	Failure to achieve at least PR, but no evidence of progression for >8 weeks
Failure	Death during treatment or disease progression characterized by worsening of cytopenias, increase in percentage of bone marrow blasts, or progression to a more advanced MDS FAB subtype than pretreatment
Relapse after CR or PR	At least 1 of the following: Return to pretreatment bone marrow blast percentage Decrement of ≥50% from maximum remission/response levels in granulocytes or platelets Reduction in Hgb concentration by ≥1.5 g/dL or transfusion dependence
Cytogenetic response	Complete Disappearance of the chromosomal abnormality without appearance of new ones
	Partial At least 50% reduction of the chromosomal abnormality
Disease progression	For patients with: Less than 5% blasts: ≥50% increase in blasts to >5% blasts 5%-10% blasts: ≥50% increase to >10% blasts 10%-20% blasts: ≥50% increase to >20% blasts 20%-30% blasts: ≥50% increase to >30% blasts
	Any of the following: At least 50% decrement from maximum remission/response in granulocytes or platelets Reduction in Hgb by ≥2 g/dL Transfusion dependence
Survival	Endpoints: Overall: death from any cause Event free: failure or death from any cause PFS: disease progression or death from MDS DFS: time to relapse Cause-specific death: death related to MDS

See footnotes on following page

Deletions to IWG response criteria are not shown.

To convert hemoglobin from grams per deciliter to grams per liter, multiply grams per deciliter by 10. MDS indicates myelodysplastic syndromes; Hgb, hemoglobin; CR, complete remission; HI, hematologic improvement; PR, partial remission; FAB, French-American-British; PFS, progression-free survival; DFS, disease-free survival.

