### 9.5.2 Secondary Efficacy Endpoints

The following analyses for the secondary endpoints will be performed for the Safety set for the Phase 1 Portion and ITT and EE set for the Phase 2 Portion of the study, respectively.

CR Rate, HI rate, and Rate of transformation to AML will be summarized descriptively by treatment arm or dose level. The corresponding 90% confidence intervals for the difference in rate between the 2 treatment arms will be provided for the 2 Portion of the study.

The number and percent of subjects with disease response of CR, Marrow CR, PR, stable disease [SD], PD or Relapse from CR / PR as collected on the Response Assessment CRF form will be presented at each visit by treatment arm or dose level.

Time-to-event variables (DOR, PFS, and OS) will be summarized descriptively using the Kaplan-Meier methodology using the SAS LIFETEST procedure. Medians and quartiles and their two sided 90% CI using the complementary log-log transformation method will be calculated, where possible. PFS probability at 3, 6, 9, ...51 months with corresponding CIs will be reported. . Kaplan-Meier figures will be presented by treatment arm or dose level.

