#### 9.5.2.1 Duration of Response

DOR (for PR/CR and CR) is defined as the time from first observation of response (PR+CR/Marrow CR or CR/Marrow CR) to disease progression/relapse or death from any cause, whichever occurs first. Durations will be assessed in the ITT population with a PR or CR and calculated separately for subjects with CR/Marrow CR and those with PR+CR/Marrow CR combined. For subjects with a remission without subsequent disease progression/relapse or death on study, DOR will be censored at the time of the last disease assessment demonstrating a lack of disease progression/relapse. Subjects who receive another antineoplastic therapy in the absence of documented progression will be censored at the time of receiving off-protocol therapy for malignancy, EXCEPT that subjects who receive stem cell transplant in remission will continue to be followed for progression. Subjects who do not have a subsequent response assessment after their first observation of response will be censored at that date (day 1).

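### SAP Table 2 omits relapse from the event rules for DOR and PFS, contradicting the SAP's own definitions, and nothing says which text prevails

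*SAP*

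**What the plan says.** SAP 9.5.4 states: "For time-related endpoints, DOR and PFS will follow" Table 2. The rows of that table that matter here are:

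- Event: "PD documented during or between scheduled visits", dated at the assessment that shows PD.
- Event: "Death before first PD assessment", and death between response assessment visits.
- Censored: "No documented progression", at the last adequate response assessment.
- Censored: "New subsequent cancer therapy initiated prior to documented progression", at the start of the new therapy.

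No row mentions relapse.

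Elsewhere relapse counts. SAP 9.5.2.1 has DOR run from first response "to disease progression/relapse or death from any cause, whichever occurs first". The PFS definition (SAP Section 5 and 9.5.2.2) and Protocol 13.6.4.2 use the same event. For subjects without an event, these sections censor at the last assessment showing neither progression nor relapse.

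Relapse also appears to be recorded apart from PD. SAP 9.5.2 ends its list of response categories with "PD or Relapse from CR / PR as collected on the Response Assessment CRF form", and Protocol Appendix 6 (18.6) has a row "Relapse after CR or PR" separate from its disease progression row.

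**The concern.** Table 2 is the row-by-row rule set that a programmer would code from, and SAP 9.5.4 says both endpoints follow it. A responder whose assessment is recorded as relapse matches no event row, so on a literal reading that subject passes to a death, new-therapy or no-progression row. That contradicts the endpoint definitions, and the SAP has no sentence giving either text precedence.

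A later PD may not repair the omission. Treatment continues only until progression, relapse or unacceptable toxicity. Post-treatment response assessment covers only subjects without progression or relapse, and ends at either (Protocol 9.1.2, 9.4.3.1 and 10.4; SAP 3.1.2). If the subject starts another therapy after relapse, Table 2 censors there.

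Timing adds to the risk. SAP 9.5 unblinds the study for ORR once all subjects have completed or stopped short of 6 cycles, while data for the secondary endpoints are still being collected. A conflict left open could be settled with the arms known. Phase 1 DOR and PFS by dose level are exposed too, because SAP 9.5.2 applies these analyses to the Phase 1 safety set.

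**Working it through.** **Plan's own figure.** The documents state no median, hazard or event count for DOR or PFS, so there is nothing to reproduce. The check compares the texts and then illustrates the size.

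**Texts side by side, for a responder whose next assessment is recorded as relapse and not as PD**

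| Source | Treatment of the relapse |
|---|---|
| SAP Section 5, 9.5.2.1, 9.5.2.2 | Event at the relapse |
| Protocol 13.6.4.2, to which 13.6.1 refers censoring | Event at the relapse |
| SAP Table 2, read literally | Not an event; outcome set by later death, new therapy or last assessment |

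SAP 1.1 lists changes from the protocol, and dropping relapse is not among them.

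**Size for DOR: simple bound.** Assume exponential durations with a true median of 12 months, and let f be the share of response-ending events coded only as relapse. If every relapse is independently censored when it occurs, the hazard falls from λ to (1 − f)λ and the median becomes 12/(1 − f):

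- f = 10%: 12/0.90 = 13.3 months
- f = 25%: 12/0.75 = 16.0 months
- f = 50%: 12/0.50 = 24.0 months
- f = 75%: 12/0.25 = 48.0 months

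**Size for DOR: Table 2 applied literally.** Here a death after an uncounted relapse is still an event. The simulation used 200,000 responders per scenario and assumed:

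- no PD is recorded after relapse;
- 0%, 50% or 100% of relapsed subjects start new therapy one month after relapse and are censored then;
- median survival after relapse is 6 or 12 months;
- data are cut off at 36 months.

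Apparent Kaplan-Meier median in months (true value 12), shown for post-relapse median survival of 6 / 12 months:

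| f | No new therapy | 50% new therapy | 100% new therapy |
|---|---|---|---|
| 25% | 14.2 / 15.5 | 14.8 / 15.7 | 15.6 / 15.9 |
| 50% | 16.7 / 19.8 | 18.5 / 21.1 | 22.1 / 23.3 |
| 75% | 19.0 / 24.5 | 23.0 / 28.3 | not reached |

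One simplification is that relapsed subjects still alive and untreated at 36 months were censored at 36 months, whereas Table 2 would use their last response assessment. Re-running with censoring at the relapse lowers individual entries by at most 2 months and leaves the 25% and 50% ranges essentially unchanged.

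**Between arms.**

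- *DOR.* With exponential times and the same f in both arms, the bound gives hazards (1 − f)λ₁ and (1 − f)λ₂. Their ratio is still λ₁/λ₂, so both medians lengthen but the comparison is not biased by this alone.
- *PFS.* Only responders can relapse. At the planning rates with 53 per arm, expected responders are 0.30 × 53 = 15.9 and 0.55 × 53 = 29.2. More subjects in the experimental arm could have an uncounted event, so a bias in its favour is plausible. The documents do not allow it to be sized.

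**The case against.** The strongest reply is that PD in Table 2 is shorthand. Every endpoint definition names relapse. SAP 9.5.2.1 and 9.5.2.2 allow censoring only at an assessment showing neither progression nor relapse, so a relapse visit cannot be a censoring date. Protocol 13.6.1 points to a section where relapse is an event, and Table 2 sits under dropouts and missing data. This stands as the likely intention. It does not remove the conflict, because SAP 9.5.4 says without qualification that both endpoints follow the table. The table departs from the definitions elsewhere too: its new-therapy row lacks their exception for transplant in remission.

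A second reply is that Appendix 6 makes the two categories overlap. A fall of at least 50% in granulocytes or platelets, and transfusion dependence, appear under both. The clear gap is a hemoglobin fall of 1.5 to less than 2 g/dL. Sites may therefore code many relapses as PD, and the CRF itself is not among the documents. This limits the likely size, but it would also make an event depend on which category the site picks.

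Three stronger readings are tempting and are not supported:

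- *That the plan requires relapses to be censored.* It does not: the definitions say the opposite, and Table 2 still counts a later PD or death.
- *That DOR would be overstated several-fold.* If deaths were 20% to 50% of response-ending events and all the rest were relapses censored on the spot, the median would be multiplied by 1/0.20 = 5 down to 1/0.50 = 2. That sets the PD share to zero and ignores deaths after relapse; nothing in the documents supports it.
- *That Marrow CR responders need a separate rule because relapse is defined only after CR or PR.* Appendix 6's progression criteria already cover them, and Table 2 counts PD. Ending their DOR by the row for less than 5% blasts alone would drop the cytopenia and transfusion criteria and miss subjects at exactly 5%.

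**Conclusion.** The inconsistency is real. Table 2 omits relapse, the definitions include it, and the SAP gives no order of precedence. The defect is a risk of mis-programming, not a settled rule that relapses are censored.

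If Table 2 were coded literally, DOR and PFS would be biased upward. For DOR, the illustration gives about 14 to 16 months at a 25% relapse share and 17 to 23 months at 50%. These figures rest on assumed exponential times, an assumed 12-month true median and the post-relapse assumptions listed. The relapse share drives the result and is not in the documents, so the bias could be small or large. A between-arm bias is plausible for PFS. For DOR it would need relapse shares that differ by arm.

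The primary endpoint, ORR, is untouched. DOR and PFS are secondary: SAP 9.5.2 summarises them descriptively, although the protocol synopsis also plans a stratified log-rank test. This is a consistency correction to make before database lock.

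**What to change.** In SAP Table 2:

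- Event row: replace PD with *PD or relapse*, identified by the Response Assessment CRF answers PD or Relapse from CR / PR, and dated at the first assessment showing either.
- No-progression and new-therapy rows: replace progression with *progression/relapse*.
- Death rows: make them deaths with no earlier *progression/relapse*.

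Add one sentence to SAP 9.5.4 stating that the definitions in 9.5.2.1 and 9.5.2.2 prevail over Table 2 where they differ. No separate Marrow CR rule is needed.

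The cost is SAP wording only, with no new data and no change to the protocol definition. Reported DOR and PFS may be shorter than under a literal reading of the table, but they will be the endpoints that the protocol defines.

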10.4 Follow-Up

If study treatment is discontinued prior to disease progression or relapse, bone marrow samples will be obtained from assessments conducted every 4 months through 24 months after EOT or until initiation of another anticancer treatment, progression, or relapse.

Events of sinusoidal obstruction syndrome/veno-occlusive disease (SOS/VOD) that occur within 180 days of the last dose of vadastuximab talirine or blinded study drug will be reported to the Sponsor, regardless of causality. Patients who undergo subsequent allo-SCT within 180 days of the last dose of vadastuximab talirine or blinded study drug in the absence of relapse and additional therapy will be followed for SOS/VOD for 100 days post-transplant.

Subjects will be contacted for survival information and collection of subsequent anticancer treatment information approximately every 2 months until death or study completion.

If subjects become candidates for stem cell transplant after enrollment, initiation of preparative regimen for stem cell transplant should not be performed until at least 30 days after the last dose of vadastuximab talirine. It is recommended to avoid transplant conditioning regimens with higher risk of SOS/VOD, including total-body irradiation and multiple alkylating agents. [27, 28] An association of SOS/VOD in patients with pre-exposure to vadastuximab talirine has not been established.

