**Progression-Free Survival:** PFS is defined as the time from first dose of study medication to first documentation of disease progression/relapse, or to death due to any cause, whichever occurs first. For subjects without disease progression/relapse or death on study, PFS will be censored at the time of the last on-study disease assessment demonstrating a lack of disease progression/relapse. If more than one date of progression is available, the earliest date will be used to determine PFS. Subjects who receive another antineoplastic therapy in the absence of documented progression will be censored at the time of receiving off-protocol therapy for

malignancy, EXCEPT that subjects who receive stem cell transplant in remission will continue to be followed for progression.

**Relative Dose Intensity (RDI):** is defined as the absolute dose intensity over the intended dose intensity,

$$\text{RDI} = \text{ADI} / \text{IDI} * 100.$$

Where IDI (intended dose intensity) is defined as the intended dose of drug (mg/kg) per unit of time.

**Study Drug:** The study drug is vadastuximab talirine (SGN-CD33A) for the study.

**Serious AE (SAE):** is defined as an answer of “Yes” for the question “Was this Serious” in CRF form of “Adverse Events and Pre-Existing Conditions”.

**Time Since Initial Diagnosis:** is defined as

Date of first dose – date of initial MDS diagnosis + 1.

**Transformation to AML:** is defined as an answer of “Yes” for the question “Has the patient progressed to AML” in CRF form of “Follow-Up”.

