#### 9.5.2.2 Progression-Free Survival

PFS is defined as the time from first dose of study medication to first documentation of disease progression/relapse, or to death due to any cause, whichever occurs first. For subjects without disease progression/relapse or death on study, PFS will be censored at the time of the last on-study disease assessment demonstrating a lack of disease progression/relapse. If more than one date of progression is available, the earliest date will be used to determine PFS. Subjects who receive another antineoplastic therapy in the absence of documented progression will be censored at the time of receiving off-protocol therapy for malignancy, EXCEPT that subjects who receive stem cell transplant in remission will continue to be followed for progression. Subjects who do not have a post-baseline response assessment after will be censored at baseline (day 1).

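### The SAP's Table 2 censors PFS and DOR at any new cancer therapy, omitting the transplant-in-remission exception that the protocol and the SAP text both state

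*SAP*

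**What the plan says.** **The rules table.** SAP 9.5.4 introduces Table 2 with "For time-related endpoints, DOR and PFS will follow", so the table is meant to be applied to both endpoints. Its row "New subsequent cancer therapy initiated prior to documented progression" assigns the start date of the new therapy and the outcome censored. Neither the row nor a footnote mentions transplant.

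**The endpoint definitions.** SAP 9.5.2.2 also censors PFS at off-protocol anti-neoplastic therapy given without documented progression, but it adds "EXCEPT that subjects who receive stem cell transplant in remission will continue to be followed for progression". The same exception stands in SAP 5.0 under Progression-Free Survival, in SAP 9.5.2.1 for DOR, and in protocol 13.6.4.2 for both endpoints.

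**Whether the case can arise.** Protocol 9.4.2 excludes subjects who are transplant candidates at screening, and protocol 9.5.3 does not allow allogeneic transplant during the study treatment period. Protocol 10.4 nevertheless plans for later transplant, in a paragraph that begins "If subjects become candidates for stem cell transplant after enrollment". Protocol 9.5.1.4.3 and 12.1.4 also provide for it.

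**The concern.** The analysis plan contains two censoring rules for the same subject. A programmer working from Table 2 and one working from 9.5.2 would derive different times, and possibly different event indicators, for a responder who goes to transplant in remission. Both could claim to have followed the SAP.

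PFS and DOR are named secondary comparisons for Phase 2. Under SAP 9.5.2 the time-to-event summaries also cover the Phase 1 Safety set by dose level, so the conflict reaches both portions. The subjects concerned are all in remission when they are transplanted. If remission is more common in one arm, the discarded follow-up may be unequal between arms. The documents do not allow the direction of any resulting bias to be stated.

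**Working it through.** The plan gives no event count, power or transplant rate for PFS or DOR, so there is no figure to reproduce. Its only Phase 2 power statement (85% with 106 subjects) concerns ORR and has no bearing here. The check is a comparison of rules.

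**Step 1. Does transplant fall inside the Table 2 row?** Table 2 does not define new subsequent cancer therapy. The definitions write transplant in remission as an exception to the rule on off-protocol therapy. An exception is needed only if transplant would otherwise be covered, so the SAP's own text places transplant within the class that Table 2 censors.

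**Step 2. Apply both rules to one subject.** Measure time from first dose. Let R be the first response, T the transplant in remission (T > R), P a later progression or relapse, D a later death without progression, and L the last disease assessment showing no progression (L > T).

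| Course after transplant | SAP 9.5.2.1 and 9.5.2.2, protocol 13.6.4.2 | Table 2, new-therapy row |
|---|---|---|
| Progression at P | PFS = P, event; DOR = P − R, event | PFS = T, censored; DOR = T − R, censored |
| Death at D | PFS = D, event; DOR = D − R, event | PFS = T, censored; DOR = T − R, censored |
| Neither, last assessed at L | PFS = L, censored; DOR = L − R, censored | PFS = T, censored; DOR = T − R, censored |

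The first two courses lose an event. The third loses follow-up of length L − T. For the first two, Table 2 also has rows that count PD and death as events, but it gives no order of precedence among rows. The table therefore does not resolve the conflict itself.

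**Step 3. Is the difference a declared change?** SAP 1.1 lists changes from the protocol. It covers the presentation of disposition and the inability to calculate hematologic improvement, and says nothing about transplant or censoring. The SAP text also repeats the protocol's exception, so the table row reads as an omission and not as a decision.

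**Step 4. How many subjects?** The documents give no rate of transplant after enrollment. The screening exclusion points to a small number, but any count would be a guess.

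**The case against.** **The intent is clear and the effect small.** The exception is stated consistently in the protocol and in three places in the SAP, so a careful programmer would probably apply it. Transplant candidates are screened out, transplant cannot occur on study treatment, and SAP 9.5.2 summarises DOR and PFS descriptively, although the protocol synopsis mentions a stratified log-rank test. All of this stands and limits the importance of the point. It does not remove the conflict, because 9.5.4 names the table as the rule to follow.

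**Follow-up after transplant may be thin.** Protocol 10.4 ends scheduled marrow assessments when another anticancer treatment starts, and does not say whether transplant in remission counts as one. If it does, the two rules may differ less in practice. They would still differ for deaths and for any progression that is recorded.

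**A stronger reading that the documents do not support.** A reader might infer that Table 2 also wrongly censors transformation to AML. Transformation comes from a Follow-Up CRF item ("Has the patient progressed to AML"), whereas the Table 2 progression event is dated by "Date of response assessment demonstrating PD". For PFS, the blast criterion "10%-20% blasts: ≥50% increase to >20% blasts" means that a baseline of 16% needs 1.5 × 16 = 24%, and 19% needs 1.5 × 19 = 28.5%. The inference fails as a finding of error for these reasons:

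- No section makes transformation a PFS or DOR event. It is a separate secondary endpoint.
- SAP 9.5.2 reports "PD or Relapse from CR / PR as collected on the Response Assessment CRF form", so the recorded response category is the source. Nothing shows that PD would go unrecorded when AML is diagnosed.
- Protocol Appendix 18.6 also allows progression by loss of granulocytes or platelets, by a hemoglobin fall, or by transfusion dependence.
- A 20% threshold for AML is inferred, not stated. At 20% the gap starts at a baseline of 20/1.5 = 13.3%. At 30% it would start at 30/1.5 = 20%, which no eligible baseline (below 20%) reaches.
- For DOR the blast gap does not arise. Responders have blasts of at most 5%, or a PR with blasts at least halved from below 20%, hence below 10%. A rise from there to 20% always exceeds 50%.

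No count of affected subjects can be drawn from the documents, and no section shows that a transformation date is collected. What remains is a question for the sponsor.

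**Conclusion.** The contradiction on transplant is real. Table 2, as written and as invoked by SAP 9.5.4, gives a different PFS and DOR result from the definitions in protocol 13.6.4.2 and SAP 5.0, 9.5.2.1 and 9.5.2.2 for any subject transplanted in remission. This rests on one reading, that transplant belongs to the class of new cancer therapy, and the SAP's exception wording supports it. The size is unknown and probably small. Only secondary endpoints are affected; ORR is not. The conflict should be removed before database lock, because it leaves the choice of result to whoever programs the endpoint.

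The verdict does not extend to AML transformation, where the plan is at most silent on one case.

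**What to change.** In the new-therapy row of SAP Table 2, add: except stem cell transplant in remission, which is not censored; follow-up for progression continues. The ordinary PD, death and no-progression rows then apply to these subjects, and the table agrees with the protocol and the SAP text.

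The cost is one line in the SAP. The endpoint definitions do not change. Protocol 10.4 already provides for collecting subsequent anticancer treatment, and response status is on the Response Assessment CRF. The sponsor should confirm that disease assessments after transplant in remission are captured, given the stopping point for marrow assessments in protocol 10.4.

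Optionally, ask the sponsor to state whether AML recorded on the Follow-Up CRF without a PD assessment counts as a PFS event. This is a request for clarification, not a correction.
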